Adverse Event (AE) Definitions. Any negative event subsequent to signing consent but prior to the week 13 visit will be considered a potential adverse event to be addressed and followed, regardless of whether it is related to use of study medication. Examples of AEs include: (1) Clinical signs and symptoms, (2) Abnormal test results, (3) Worsening of existing medical conditions. The licensed medical professional (LMP) will consider adverse events serious if the event: (1) is life threatening, (2) results in death, (3) leads to incapacity, hospitalization, or serious impairment of normal life, (4) congenital abnormality or birth defect. Serious AEs will be reported to the IRB within 24 hours of the site becoming aware of the event. Once an adverse or serious adverse event is identified, it must be followed and recorded, such that subsequent to the designation each event

outcome should be characterized as follows: 1 = Still present, 2 = Resolved with Sequelae, 3 = Resolved without Sequelae, 4 = Lost to follow-up/Unknown, 5 = Death.

Determination of Severity. The study coordinators will make a determination of AE severity and provide a grade for each event according to the following criterion: Mild: Symptoms cause little discomfort, are easily tolerated, and do not significantly interfere with normal everyday activities. Moderate: Symptoms are uncomfortable and interfere with normal everyday activities. Severe: Symptoms cause significant impairment of everyday activities, incapacitation, or death

Determination of Causality. The LMP will make a determination the causality of each adverse event in relation to the study medication using the following criteria: 1 = Definite, 2 = Probable, 3 = Possible, 4 = Remote, 5 = Definitely Not

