Process for Handling AEs. At each visit and post-cessation call (and via EMA, see sub-study below), every participant will be asked to report on health status and adverse events. In addition, study participants will be instructed verbally and in writing to contact the study staff immediately if any health problem causes disruption in the participant's life — though participants will be informed to call 911 if they are experiencing any potentially life-threatening problems. Calls to the study staff will be triaged to determine if the study LMP should be contacted. The Arizona State University and LACT study physicians will address any medical problems that might arise (including working with each participant's health care provider if needed).

AE Reporting Period. All events not resolved or unrecovered by week 13 will be followed for 30 days after that date to assess status. Any participants lost to follow-up after a reported AE or serious AE will have 'unknown' indicated for that event.

Participant Payment

Main Study and Sub-studies. Note that all study participants will receive compensation for time and/or travel to the study sites as well as completing telephone visits during the treatment and follow-up study phases. Participants in the in-person cohort will be paid \$50 compensation for the screening/baseline visit, \$25 compensation for completing each of the weeks 2 and 13 telephone visits, \$50 for completing the in-clinic visits at weeks 4 and 8, and \$100 for completing the in-clinic week 12 visit (total of \$250), regardless of their smoking status. In addition, study participants will be compensated \$50 to come into the study sites to complete electronic questionnaires and to provide a breath CO if they report 7-day point prevalence abstinence at the 6-month follow-up call. Given the attrition that occurs in many smoking cessation studies, especially those that assess OTC medications, compensation for key study visits is essential.

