Data Sharing Plan. The information that we will collect includes medically-related information that is protected and must remain confidential, so all standard methods to protect participant confidentiality will be employed, including maintaining information in password protected encrypted databases to reduce the risk of a data breach. Shared data across the two study sites will likewise be password protected and encrypted. After study completion, any outside requests for data will require a data sharing agreement that assures the following: (1) all data must be maintained in a secure fashion using appropriate technology, (2) commitment to use the data only for the research purposes requested, and (3) all shared data must either be destroyed or returned, including written assurances to that effect.

Statistical Analysis Plan

Main study. The participation flow will be reported following CONSORT guidelines. Intention to treat analysis will be applied for all statistical analyses. The data collected from the study will be summarized by the descriptive statistics for overall and by treatment condiction (1mg b.i.d., .5mg b.i.d. and placebo) and by the application of EMA (yes/no). The primary analysis will include estimating and comparing the guit rates between treatment arms. We will fit a logistic regression to model the probability of smoking cessation at 12 weeks with treatment condition, application of EMA and the interaction term of the two main effects as independent variables. If the interaction term is not significant, this implies the guit rates for the same treatment condition are similar in those with and without the utilization of EMA, and we will drop the interaction term and fit a model with main effects only. The comparison will be perfromed by the Wald test from the logistic regression with Bonferroni adjustment to account for multiple comparisons. The point estimate of guit rate and 95% confidence interval (CI) for each treatment condition will be reported. If the interaction term is significant, we will conduct the comparisons in EMA and non-EMA subgroups. A similar approach will be applied to the analysis of adherence and adverse events. These two outcome variables can be analyzed as a dichotomous (yes/no) or count variable (pill count and number of adverse events), and the logistic regression and Poisson regression will be used to evaluate whether group differences occur. In the secondary analysis, to evaluate

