the impact of participant characteristics on the study outcomes, we will fit multivariable logistic or Poisson regression models. The odds ratio (from logistic regression) and ratio or percent change (from Poisson regression) will be reported to quantify the association.

In addition to evaluting the primary and secondary outcomes at the end of treatment (12 week), the trend over time between the initiation of treatment and at the end of the follow up period is also of interest. We will implement generalized linear mixed model (GLMM) with random intercept to account for the clustering effect (multiple visits clustered within each participant). Independent variables will include treatment condition, visit number, and other time-varying characteristics collected post radomization. We intend to use two-level GLMMs, and will perform exploratory analysis using 3-level GLMMs (visits clustered within participants, and participants clustered within sites [CA, AZ]), as we anticipate the variability from sites would be negligible.

Analysis of the Remote Cohort. We will assess the in-person and remote cohort data via separate analyses, but because the fundamental study design in the same for both, if the outcomes of the separate analyses suggest similar outcomes, we might combine the results of both groups into a single analysis.

EMA Statistical Analysis Plan. Our approach to analyzing EMA data is based on published approaches^{32,33} using GLMMs. This class of models is useful for analyzing EMA data because they allow multiple observations per subject, multiple levels of nesting (i.e., observations within weeks within subjects), multiple subject random effects, modeling of between-subjects (BS) and within-subjects (WS) variance as a function of time-invariant covariates (e.g. treatment assignment, gender, or nicotine dependence), and extension to non-normal outcomes (i.e., dichotomous, ordinal, counts). Our primary approach will be a three-level mixed model treating observations (level 1) within days (level 2) within subjects (level 3). Additionally, we will employ a time-varying effect model (TVEM)³⁴ if we find evidence that the relative association between momentary medication adherence, side effects, craving, and smoking varies over the two weeks of observation.³⁵ We present brief examples of analyses of central interest below.

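### Adverse-event counts are compared by Poisson regression with no allowance for time observed, so the ratio between arms is distorted if loss to follow-up differs by arm

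*Combined protocol and SAP*

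**What the plan says.** Under Statistical Analysis Plan, Main study, adherence and adverse events are handled by an approach similar to the quit-rate model, whose terms are treatment, EMA and their interaction. On the form of the outcome: "These two outcome variables can be analyzed as a dichotomous (yes/no) or count variable (pill count and number of adverse events"). On the model: "the logistic regression and Poisson regression will be used to evaluate whether group differences occur". The analysis set is everyone randomised: "Intention to treat analysis will be applied for all statistical analyses". For the participant-characteristics models that follow, "The odds ratio (from logistic regression) and ratio or percent change (from Poisson regression) will be reported to quantify the association"; no person-time denominator is named there either.

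On collection, Adverse Event Definitions sets the period: "Any negative event subsequent to signing consent but prior to the week 13 visit will be considered a potential adverse event". Process for Handling AEs says that at each visit and call "every participant will be asked to report on health status and adverse events". Participant Payment explains why visits are paid: "Given the attrition that occurs in many smoking cessation studies, especially those that assess OTC medications, compensation for key study visits is essential".

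The only rule on loss to follow-up for adverse events, under AE Reporting Period, codes the outcome of an event already reported as unknown. Nothing covers events that were never collected.

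**The concern.** A participant lost at week 4 can report about four weeks of events, and one who stays can report about thirteen. With everyone randomised in the model and no term for time observed, a short observation enters as a low count. The ratio between arms then mixes the event rate with retention. This affects the point estimate and is separate from any question about the variance of the counts.

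Safety is part of both primary objectives, and Hypothesis 3 expects a dose response with placebo lowest. If an active arm lost more people, the comparison would understate harm; if placebo lost more, it would overstate harm. In both cases the dose pattern would be partly a pattern of retention.

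**Working it through.** **The plan's own figure.** The documents give no expected figure for the adverse-event comparison. The stated 110 per group concerns quit rates; it reproduces (23% versus 8%, two-sided 0.025, 80% power) and is not affected by this point.

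**Inputs.** From the documents: a counting period of nominally 13 weeks, events asked about at contacts, 1:1:1 allocation, and 432 / 3 = 144 per arm. Assumed, because the documents give none: 0.3 events a week in weeks 1-2 and 0.1 a week afterwards on placebo, all losses at week 4, and true ratios of 1.00 and 1.30.

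**Expected count per placebo-rate participant.**
- Full follow-up: 2 × 0.3 + 11 × 0.1 = 1.7.
- Lost at week 4: 2 × 0.3 + 2 × 0.1 = 0.8.
- Arm with fraction d lost: (1 − d) × 1.7 + d × 0.8. This gives 1.565 at 15%, 1.52 at 20%, 1.43 at 30% and 1.34 at 40%.

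**Ratio without an offset** = true ratio × (active count / placebo count at equal rates).

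| Lost, active vs placebo | Retention factor | True 1.30 becomes |
|---|---|---|
| 30% vs 15% | 1.43 / 1.565 = 0.914 | 1.19 |
| 40% vs 20% | 1.34 / 1.52 = 0.882 | 1.15 |
| 15% vs 30% | 1.565 / 1.43 = 1.094 | 1.42 |
| 20% vs 20% | 1.000 | 1.30 |

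**Single whole-trial offset.** Mean weeks observed are (1 − d) × 13 + d × 4: 10.3 at 30% lost and 11.65 at 15%. The factor becomes (1.43 / 10.3) / (1.565 / 11.65) = 1.033. For 40% versus 20% it is (1.34 / 9.4) / (1.52 / 11.2) = 1.050. So a single offset errs by 3% to 5% in the other direction when events cluster early.

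**Interval-level model.** Within each contact interval, the people still observed have the same rate ratio in both loss groups. With interval as a factor and log days observed as offset, the model therefore estimates the true ratio, provided that loss is unrelated to a person's own events.

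**Effect on tests** (simulation under the same rates, 144 per arm, two-sided 0.05 for illustration):
- 30% versus 15% lost, true ratio 1.00: about 17% false positives without an offset, 5% with the interval model.
- 30% versus 15% lost, true ratio 1.30: power about 49% without, 82% with.
- 40% versus 20% lost, true ratio 1.30: power about 34% without, 81% with.
- 20% lost in both arms: both methods give 1.30 with about 83% power.

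**Sensitivity to the assumptions** (13 weeks, 40% active versus 20% placebo lost):
- Constant event rate, losses spread evenly: factor (1 − 0.40/2) / (1 − 0.20/2) = 0.889.
- Constant rate, all losses at day 14: 0.796.
- Event rate decaying with a 21-day constant, losses spread evenly: 0.955 without an offset, 1.074 with a simple one.

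**The case against.** The strongest reply is that the bias is conditional and its key premise is not documented. That stands. With equal loss unrelated to events the ratio is unbiased. The documents give no dropout rate, overall or by arm. The payment section speaks of attrition in general and gives no cause. A reader might infer that side effects will empty the 1 mg arm, or lack of effect the placebo arm. The documents say neither, and the two would push in opposite directions. Appendix 10 does list side effects and lack of effect as reasons for not using medication as directed, but that concerns pill use. Protection Against Risks says that participants are followed after stopping medication, so stopping pills does not by itself end observation. Paid visits and CONSORT flow reporting also help.

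It is also fair that the plan is silent on an offset and does not exclude one. Silence still leaves the choice open until the data are seen. The visit-level mixed model does not fill the gap: it is an additional analysis of trend and states no offset.

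The sample-size section's expected rise in side effects over the first five days concerns severity and odds in the EMA sub-study. It does not establish that 13-week event counts cluster early, so early clustering is an assumption here.

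Finally, the interval model is no complete cure. Suppose that event rates vary between people (gamma, shape 1), 30% of active and 15% of placebo are lost at week 4, and active participants with an event in weeks 0-4 are three times as likely to be lost. A true 1.00 is then estimated as 0.87 by the raw count, about 0.95 by the interval model and about 0.98 by the single offset. A true 1.30 is estimated as 1.13, about 1.23 and 1.28. Both offset models beat the raw count, and here the single offset comes closer. With 30% lost in both arms under the same mechanism, the interval model still gives about 0.95 and 1.24.

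**Conclusion.** The omission is real: the adverse-event group comparison has no term for time observed and no rule for people lost early. Whether it produces bias depends on observed time differing between arms. Under the assumed rates with week-4 losses, differences of 15 to 20 percentage points move a true 1.30 to between about 1.15 and 1.42; with equal loss unrelated to events it stays at 1.30. Direction and size cannot be fixed from the documents.

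A reader might go further and conclude that this trial's adverse-event ratio is biased, or that the plan will hide harm. The documents do not support either conclusion, because they do not show that loss will differ by arm or why people will leave. What they support is a plan that should be completed before the data are analysed. The yes/no logistic form needs the same attention, since a person lost early also has less time to report a first event.

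**What to change.** In the Main study analysis text:

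1. State that adverse-event counts are modelled by Poisson regression with log(time observed) as offset. Preferably use one record per participant per contact interval, with interval as a factor, log(days observed in the interval) as offset and standard errors clustered by participant.
2. For the yes/no form, compare events within a fixed early window, or use time to first event.
3. Report time observed by arm.
4. State one time origin, one end of counting, and how days are credited when a contact is missed and a later one is completed. The following must be reconciled: Adverse Event Definitions counts from consent and stops before the week 13 visit; Tables 1 and 3 mark adverse events at week 26; Table 2 counts days from randomization and puts weeks 12 and 13 at days 98 and 105; remote visits run from medication start.
5. Add a sensitivity analysis for people leaving because of their own adverse events, with the single-offset result alongside, because an offset reduces that bias without removing it.

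The cost is plan wording and a little programming. Adverse events are already recorded by contact, no new data are needed, and the sample size does not change. If loss proves equal and unrelated to events, almost no precision is given up.

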- 1. To assess the safety and efficacy of the current FDA-approved 1 mg b.i.d. varenicline for smoking cessation in comparison with placebo when used in a simulated OTC study with no behavioral support provided.
- 2. To assess the safety and efficacy of .5mg b.i.d. varenicline in comparison with 1mg b.i.d. varenicline and placebo when used in a simulated OTC study with no behavioral support provided.

Secondary Objectives

- 1. To evaluate whether subject specific characteristics (e.g. socioeconomic status, ethnicity, smoking history, etc.) moderate primary (safety and efficacy) and secondary (adherence) outcomes.
- 2. To evaluate medication use patterns to assess whether varenicline is being used as indicated on the label, and to determine if medication adherence mediates cessation outcomes between-subjects.

3. In a subsample of participants, to examine how medication adherence, withdrawal, and side effects (e.g. nausea and sleep disturbance) vary within-subjects and are associated with smoking status using EMA in the first two critical weeks of medication use.

[figure not shown]
Hypotheses

- 1. Quit rates in the 1 mg b.i.d. varenicline condition will be significantly higher than the placebo medication condition when provided as an OTC medication.
- 2. Quit rates in the .5 mg b.i.d. varenicline condition will be comparable to the 1mg b.i.d. varenicline condition, and will be significantly higher than the placebo medication condition, when provided as an OTC medication.
- 3. Side effects will show a dose response relationship, with effects lowest in the placebo group.

C. EXPERIMENTAL METHODS Study Design

The primary objective of this study is to assess the efficacy of two different doses of varenicline used in a simulated OTC intervention relative to placebo (total N = 432). The design is a three-group placebo-controlled, double blind, block randomized clinical trial (as indicated in the figure), where participants will be randomly assigned to one of three

conditions: (1) 1 mg b.i.d. varenicline for 12 weeks, which is the current FDA-approved dose, (2) 0.5 mg b.i.d. varenicline for 12 weeks, or (3) placebo.

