- Adverse Events
- Concomitant Medications
- Smoking Status and Resource Utilization Assessment (See Appendix 9) (Brief site administered questionnaires assessing smoking status, smoking cessation resources used since last study visit
- Medication Adherence, and Perceived Efficacy Assessment (see Appendix 10) (Brief site administered questionnaires assessing pills taken since last study visit, and perceived efficacy of the medication.
- Modified Cigarette Evaluation Questionnaire (mCEQ), see Appendix 11). This 15item staff or subject administered questionnaire assesses the degree to which smokers experience the reinforcing effects of smoking.

Weeks 4, 8 for the In-person Cohort

- Breath Carbon Monoxide test
- Minnesota Nicotine Withdrawal Scale
- Adverse Events
- Concomitant Medications
- Smoking Status, and Resource Utilization Assessment
- Medication adherence and Perceived Efficacy Assessment
- Assess medication use by retrieving unused medication
- Modified Cigarette Evaluation Questionnaire (mCEQ)
- Dispense additional Investigational Product

*All questionnaires at this visit will take place, as much as possible, on the phone prior to the subject attending the visit as to minimize contact in response to the COVID-19 pandemic

Week 12 for the In-person Cohort

- Body weight
- Breath Carbon Monoxide test
- Minnesota Nicotine Withdrawal Scale
- Adverse Events
- Concomitant Medications
- Smoking Status, and Resource Utilization Assessment

- Medication Adherence and Perceived Efficacy Assessment
- Assess medication use by retrieving unused medication
- Modified Cigarette Evaluation Questionnaire (mCEQ)

*All questionnaires at this visit will take place, as much as possible on the phone prior to the subject attending the visit as to minimize contact in response to the COVID-19 pandemic

Week 13 (telephone call) for the In-person Cohort

- Smoking Status, and Resource Utilization Assessment
- Adverse Events
- Minnesota Nicotine Withdrawal Scale
- Concomitant Medications including Chantix[™] or other smoking cessation aids

Week 26 for the In-person Cohort

- Telephone call
- Smoking Status and Resource Utilization Assessment
- Body weight
- Breath Carbon Monoxide test

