- Minnesota Nicotine Withdrawal Scale
- Adverse Events
- Concomitant Medications
- Smoking Status and Resource Utilization Assessment (See Appendix 9) (Brief site administered questionnaires assessing smoking status, smoking cessation resources used since last study visit
- Medication Adherence, and Perceived Efficacy Assessment (see Appendix 10) (Brief site administered questionnaires assessing pills taken since last study visit, and perceived efficacy of the medication.
- Modified Cigarette Evaluation Questionnaire (mCEQ), see Appendix 11). This 15item staff or subject administered questionnaire assesses the degree to which smokers experience the reinforcing effects of smoking.

Week 4 Visit for Remote Cohort

- Minnesota Nicotine Withdrawal Scale
- Adverse Events
- Concomitant Medications
- Smoking Status, and Resource Utilization Assessment
- Medication adherence and Perceived Efficacy Assessment
- Modified Cigarette Evaluation Questionnaire (mCEQ)

Week 8 Visit for the Remote Cohort

- Urine cotinine test, if they report not smoking
- Minnesota Nicotine Withdrawal Scale
- Adverse Events
- Concomitant Medications

- Smoking Status, and Resource Utilization Assessment
- Medication adherence and Perceived Efficacy Assessment
- Modified Cigarette Evaluation Questionnaire (mCEQ)

Week 12 for the Remote Cohort

- Urine cotinine test, if they report not smoking
- Minnesota Nicotine Withdrawal Scale
- Adverse Events
- Concomitant Medications
- Smoking Status, and Resource Utilization Assessment
- Medication Adherence and Perceived Efficacy Assessment
- Assess medication use by asking the participants to mail back any unused study medication
- Modified Cigarette Evaluation Questionnaire (mCEQ)

Week 13 for the Remote Cohort

- Smoking Status, and Resource Utilization Assessment
- Adverse Events
- Minnesota Nicotine Withdrawal Scale
- Concomitant Medications including Chantix[™] or other smoking cessation aids

Week 26 for the Remote Cohort

- Telephone call
- Smoking Status and Resource Utilization Assessment
- Urine cotinine test, if they report not smoking

Visit Window for the Remote Cohort. Will be the same as shown in Table 2.

Inclusion Criteria for the Remote Cohort

- 1. 21 years of age or older
- 2. Self-reported daily smoker
- 3. Positive cotinine from urine sample
- 4. Motivated to quit smoking completely within five weeks of the Screening Visit (>5 on reported motivation)
- 5. Capable of and agree to complete study requirements

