Alternatives to Participation. Any of those who are not eligible for the study will be referred to the free smoking cessation quitline available in both states. In addition, any participants who elect to drop out of the study will also be referred to the state quitline, or could potentially obtain Chantix or another medication from their healthcare provider.

Investigational Product

Product: Varenicline (generic name, product name is Chantix™)

Doses: 0.0 mg, .5mg and 1.0 mg

Product Form: Pill

Product Administration: Oral, with water

Manufacturer: Pfizer

Varenicline and Placebo. In this study, participants will be randomly assigned in double-blind fashion to use one of two doses of varenicline (.5 mg b.i.d. or 1.0mg b.i.d.) or placebo (see study design above). Both varenicline and the placebo will look identical and be in identical packaging.

Medication Dosing. Participants assigned to the 1.0 mg b.i.d. condition, which is the current FDA-recommended dosing, will follow the recommended varenicline titrated dosing schedule as follows: days 1 through 3: 0.5mg, one daily; days 4 through 7: 0.5mg, twice daily; days 8 through end of treatment: 1mg, twice daily. Those assigned to the 0.5mg bid. condition will begin use 0.5mg once daily days 1 through 3, then will begin using 0.5 b.i.d on day 4 through the end of the study. Those assigned to the placebo condition will use pills that look identical to those that are being used in the other conditions but contain no medication. The subjects in the placebo group will also titrate during the first 7 days (1 pill days 1-3, 2 pills for the duration of the treatment period). All participants will take identical looking pills at the same time throughout the study, with the only difference being the amount of varenicline included in each pill.

Product Packaging. Medication packaging for this study will be implemented at the ASU site. Two study staff will work together to package the medications, and all packaging will be double checked and tracking forms maintained by the staff to assure quality control. Medications will be shipped by FedEx or equivalent to LACT (or directly to participants if they are participating in the study remotely), where study product will be checked and a report provided back to ASU within 24 hours indicating whether all sent medications were received.

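### If adherence is analysed as a pill count, the trend model has no scheduled-pill denominator, so unequal visit intervals distort the time trend

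*Combined protocol and SAP*

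**What the plan says.** Adherence is named as a secondary outcome in Secondary Objective 1 ("moderate primary (safety and efficacy) and secondary (adherence) outcomes"), and Secondary Objective 2 concerns medication use patterns and use as labelled.

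In section E, Statistical Analysis Plan, Main study, adherence and adverse events are treated together: "These two outcome variables can be analyzed as a dichotomous (yes/no) or count variable (pill count and number of adverse events"), with logistic or Poisson regression accordingly. The trend paragraph then begins "In addition to evaluting the primary and secondary outcomes at the end of treatment (12 week), the trend over time" and continues: "We will implement generalized linear mixed model (GLMM) with random intercept to account for the clustering effect". The predictors are given as: "Independent variables will include treatment condition, visit number, and other time-varying characteristics collected post radomization". Neither paragraph mentions an offset, exposure time or number of pills scheduled.

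The adherence data come from two sources.

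- **Questionnaire.** At weeks 2, 4, 8 and 12 in both cohorts, the visit list describes it as "assessing pills taken since last study visit, and perceived efficacy of the medication". The form in Appendix 10 records the days since the last visit and asks for the percentage of days with two, one or no doses.
- **Returned product.** Table 1 shows retrieval at weeks 4, 8 and 12 for the in-person cohort. The remote cohort returns product once, at week 12: "Assess medication use by asking the participants to mail back any unused study medication".

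On the schedule, the Medication Dosing text gives the pill pattern for the placebo group as "1 pill days 1-3, 2 pills for the duration of the treatment period" and says that all participants take identical-looking pills at the same times. Product is stated to be available for at most 12 weeks. Table 2 sets target days 14, 28, 52 and 98 for weeks 2, 4, 8 and 12.

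**The concern.** A count of pills taken between two visits depends on how many pills were scheduled between them. Here that number changes from visit to visit by design. A Poisson model of the raw count on visit number cannot tell a longer interval from better adherence. The time trend bearing on Secondary Objective 2 could then be overstated, or a decline understated, even with complete data and correct standard errors.

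A related problem concerns the cohorts. A pill count from a week-12 return spans the whole course for a remote participant but only the time since week 8 for an in-person one. The plan says that the two cohorts might be combined.

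**Working it through.** The plan states no figure for the adherence trend, so there is none to reproduce.

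**Inputs.** One pill a day on days 1-3 and two a day from day 4 (Medication Dosing). A 12-week course is 84 days, so the total is 3 × 1 + 81 × 2 = 165 pills. Visit days are 14, 28, 56 and 84 by week label, or 14, 28, 52 and 98 by Table 2.

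**Scheduled pills per interval.**

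| Schedule | to wk 2 | wk 2-4 | wk 4-8 | wk 8-12 |
|---|---|---|---|---|
| Week labels | 3 + 11×2 = 25 | 14×2 = 28 | 28×2 = 56 | 28×2 = 56 |
| Table 2, dosing ends day 84 | 25 | 28 | 24×2 = 48 | 32×2 = 64 |
| Table 2, dosing to day 98 | 25 | 28 | 48 | 46×2 = 92 |

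**Formula.** Take log E(pills) = a + b × visit number, with no offset and visit number linear. When all participants share the visits, a random intercept leaves b unchanged. The fitted ratio per visit r = exp(b) solves Σ v·r^v / Σ r^v = Σ v·y_v / Σ y_v. A constant adherence fraction cancels, so scheduled pills can be used for y.

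**Returned product, in person (weeks 4, 8, 12), constant adherence.** The first return covers 25 + 28 = 53 pills.

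- Week labels (53, 56, 56): (53 + 112 + 168)/165 = 2.018, r = 1.03.
- Table 2 ending day 84 (53, 48, 64): (53 + 96 + 192)/165 = 2.067, r = 1.105, about 11%.
- Table 2 to day 98 (53, 48, 92): (53 + 96 + 276)/193 = 2.202, r = 1.36.

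**Returned product, adherence falling 90, 85, 75, 60% over the four intervals.** Pills taken to week 4 are 0.90×25 + 0.85×28 = 46.3.

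- Week labels (46.3, 42, 33.6): r = 0.85.
- Table 2 ending day 84 (46.3, 36, 38.4): r = 0.91.
- Table 2 to day 98 (46.3, 36, 55.2): r = 1.10, a false rise.
- With log scheduled pills as offset: r = 0.83 on all three schedules.

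With dosing ending on day 84, the fall is therefore understated but keeps its sign.

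**Questionnaire converted back to pills (weeks 2, 4, 8, 12).**

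- Constant adherence, week labels (25, 28, 56, 56): (25 + 56 + 168 + 224)/165 = 2.867, r = 1.35.
- Constant adherence, Table 2 ending day 84 (25, 28, 48, 64): (25 + 56 + 144 + 256)/165 = 2.915, r = 1.41.
- Falling adherence as above: r = 1.19 (22.5, 23.8, 42, 33.6) and 1.22 (22.5, 23.8, 36, 38.4). With the offset, r = 0.87 in both. On this construction the sign is reversed.

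**Effect of a denominator.** With log scheduled pills as offset, constant adherence gives r = 1 by construction. A simulation of 432 participants with mean adherence of 80% and a between-person SD of 15 points also gave 1.00.

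**Week-12 return, full adherence.** Remote: 165 scheduled pills. In person since week 8: 56 or 64. The ratio is 165/64 = 2.6 to 165/56 = 2.9.

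**The case against.** The strongest reply is that the trial does not directly collect a four-visit pill count. The Appendix 10 form is already expressed relative to the interval, so constant adherence stays constant on it whatever the visit spacing. Physical counts exist only at weeks 4, 8 and 12 in person and at week 12 remotely. On those counts the artefact is 3-11% per visit, with no change of sign in the falling scenario when dosing ends on day 84. This stands. A reader might infer from the plan that the trend will show a 35-41% spurious rise, or that falling adherence will be reported as rising. The documents do not support that as the expected result. With dosing ending on day 84, it needs the analyst to multiply the form's percentages by interval length, and nothing says that this will be done.

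The 36% figure also needs caution. It takes Table 2's day 98 as a dosing day, against the stated maximum of 12 weeks. The in-person week-8 container holds five weeks (5 × 7 × 2 = 70 pills), short of the 92 that this reading schedules.

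Three further points stand. The plan also permits a dichotomous outcome. All arms share a schedule, so between-arm ratios within a cohort are not biased. The cohorts are to be analysed separately first, so the week-12 mismatch bears only on a combined analysis.

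Two replies do not remove the point. Unnamed time-varying characteristics might include interval length, but the plan does not say so, and a free covariate is not an offset. Fitting visit as categorical leaves the spacing effect in the visit contrasts.

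**Conclusion.** The point holds, conditional on the count option being used. The plan gives a pill count, a Poisson model and visit number as the time variable, with no denominator, while the pills scheduled per interval vary by design. For returned product in person, the spurious trend is about 3% per visit (week labels) to 11% (Table 2, dosing ending on day 84), with 36% as the reading to day 98. These figures assume linear visit number, titration counted, visits on target days and complete returns.

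The larger four-visit figures describe a risk if questionnaire percentages are turned back into counts. They are not a consequence of the plan as written. A reader might also infer that the treatment comparison or the primary endpoint is compromised. Neither follows: the artefact lies in the time trend of a secondary outcome. The cohort mismatch of 2.6-2.9 times arises only if last-interval in-person returns are combined with whole-course remote returns.

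**What to change.** In the Main study text of the Statistical Analysis Plan:

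1. Define the adherence variable for the trend model. Either model pills taken relative to pills scheduled in the same interval (Poisson with log scheduled pills as offset, or binomial taken out of scheduled), or analyse the percentage of days already recorded in Appendix 10.
2. Replace visit number with scheduled week or actual week, and state the time origin. Table 2 counts from randomization, while remote visits are timed from the medication start date.
3. Sum in-person returns over the full course before any comparison or pooling with the remote cohort.
4. Reconcile Table 2's target days for weeks 8 and 12 (52 and 98, against 8×7 = 56 and 12×7 = 84) with the week labels and the 12-week treatment period. The size of the artefact depends on which applies.

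The cost is a few sentences and one derived variable. No new data are needed. The small downside is that dispensing, return and visit dates must be merged into the adherence dataset.
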